The oval foramen remains pervious after birth in about 20% of the population and predominantly in female subjects. Closure of the oval foramen pervio (PFO) resulted in a partial or complete regression of migraine symptomatology in several retrospective and monocentric^{studies 4-6}. In these studies, percutaneous correction of PFO had been performed for the secondary prevention of stroke⁴ or for the presence of conditions related to intracardiac shunt such as decompression sickness in divers⁶. Since there are no diagnostic or provocative tests capable of correlating PFO to migraine, it is difficult to understand which patients will be responsive to the elimination of the right-left intracardiac shunt after correction of PFO.

Other possible clinical benefits of PFO closure include reducing the sequelities of a paradoxical embolism such as ischemic stroke, myocardial infarction^{11,12} and cognitive impairment.

Although it has not been documented, the prevention of chronic headache through the correction of PFO in the earliest and phase phase of the disease can also be beneficial. Current estimates indicate that 4% of the general population suffers from chronic migraine¹³ which in 75% of cases is the result of a transformation from a phasic or periodic migraine.¹⁴ Eradication of the source of migraine can also be positive against these progressive pathological processes. However, to date, international guidelines (ESC and AHA/ACC) do not include migraine among the indications to the correction of PFO.

he prevalence of PFO in subjects with migraine with aura varies between 41% and 89%⁴, while it is between 7% and 34% in symptomatic patients for migraines without aura and between 20% and 25% in controls without migraine⁴.

This association is two-way because the risk of developing a neurological ischemic event in a subject with PFO and migraine is 5.1 times higher (95% CI, 4.67 -5.59) than in a subject without PFO⁹ and young women are more frequently symptomatic for migraine when affected by PFO.

In women and patients with stable coronary artery disease, in antiplatelet therapy with aspirin, high platelet reactivity (HAPR) or resistance to aspirin has been described, which is associated with unfavorable clinical outcomes. A study conducted by Jesurum et al, suggested that subjects with migraine have a higher prevalence of HAPR than healthy subjects or patients with stable coronary artery disease being treated with aspirin 325 mg. However, the clinical implications of HAPR in subjects with emicrania and PFO require further investigation of analysis for the high risk of cerebral stroke and myocardial infarction and highlight the need to prescribe preventive antiplatelet therapy early.

Protocol number

NCT03521193

In addition, the extent of the right-left shunt as assessed and measured at the transcranial Doppler also increases progressively from the migraine-free control groups, to the migraineranics without aura and in those with aura¹⁷.

Recent studies have shown that a prominent Eustachian valve and a Chiari network, as an embryonic residue in the right atrium, are more often detectable in migraine patients with aura (100% in migraine with aura vs 55% in non-migraines)^{19,20} and this could explain the increase in dx-sin shunt. In addition, an analysis of the anatomy of the interatrial septal (SIA) showed the presence of SIA aneurysm in 13% of patients with migraine compared to 1.9% of control subjects ($p=0.05$)²¹. In addition, among migraine patients, SIA aneurysm was predominantly observed in subjects with aura (28%) compared to those without aura (3.6%)²¹.

Rational

The premium (Prospective, Randomized Investigation to Evaluate Incidence of Headache Reduction in Subjects With Migraine and PFO Using the AMPLATZER PFO Occluder to Medical Management) study hypothesis was based on the possible significant reduction in the frequency of migraine attacks with and without aura after percutaneous correction of PFO and broad dx-sin shunt in patients symptomatic for migraine from 6 to 14 days/month and not responsive to drug therapies. The primary endpoint of the study was to reduce the frequency of migraine attacks (with or without aura) by at least 50%; the proportion of patients with headache reduction was superimposable in the PFO correction group (38.5%) and in that addressed to medical therapy (32%), $p=0.32$. With regard to secondary endpoints, there was a significant reduction in the number of migraine days/month after CORRECTION of PFO compared to the control group (-3.4 ± 4.4 days versus -2.0 ± 5.0 days ($p = 0.025$)). No difference was observed in the percentage of patients who achieved a 75% reduction > migraine attacks while a very significant difference was observed with regard to subjects who experienced a complete regression of migraine episodes: 8.5% (10/117) in the PFO correction group vs 1.0% (1/103) in the medical therapy group ($p=0.01$). Among these patient responders, 6 were symptomatic for migraine with aura while the other 4 were migraines with isolated episodes of aura.

It could be speculated that the etiological mechanism of headache in patients not subjected to PFO closure could be the activation of platelets inside the tunnel, the overlap between septum primum and secundum, of the patent foramen ovale. This segment, which may be characterized by a potential flow turbulence between the two septa, could lead to platelet activation, especially in the presence of SIA aneurysm. In a small group of patients with migraine, resistance to aspirin has been documented in 24% of subjects, suggesting platelet hyper-reactivity.

Clopidogrel and aspirin are more effective than aspirin alone in reducing headache, exacerbated after percutaneous correction of PFO in the first follow-up period²⁴ to demonstrate that platelet microaggregates may be responsible for post-closure migraine of PFO and may play a central role in the genesis of headache.

In women and patients with stable coronary artery disease, in antiplatelet therapy with aspirin, high platelet reactivity (HAPR) or resistance to aspirin has been described and is associated with adverse clinical outcomes. A study conducted by Jesurum et al, suggested that subjects with migraine have a higher prevalence of HAPR than healthy subjects or patients with stable coronary artery disease being treated with aspirin 325 mg. However, the clinical implications of HAPR in subjects with migraine and PFO require further investigation of analysis for the high risk of cerebral stroke and myocardial infarction and the need to prescribe early prevention therapy.

A PFO with dx-sin shunt should require a neurological substrate susceptible and vulnerable to some substance that by-passes the pulmonary circle and induces headache. The endothelium of the

Protocol number

NCT03521193

pulmonary circle has significant metabolic activity. The lung in fact metabolizes, activates or inactivates many compounds including vasoactive amines and other humoral substances²⁵. Prostaglandins E1, E2 and F2 are completely removed from the bloodstream; serotonin is removed between 85% and 95%; 70% of angiotensin I is converted to angiotensin II, and 80% of bradykinin is inactivated²⁶. It is not known whether these substances may increase the susceptibility of the brain to stimulate environmental or intrinsic triggers capable of triggering migraine

Objectives and aims of the study

The aim of the study is to verify whether vasoactive/inflammatory substances together with increased platelet reactivity may play a key role in the onset of migraine and in its maintenance even after correction of PFO. The morphological and anatomical characteristics of the oval fossa will also be analyzed in order to identify elements that can correlate with increased platelet reactivity and predict a clear benefit in the control of migraine symptoms after correction of PFO. The analysis will also be extended to the evaluation of differences between female and male sex.

4. Study design

1. 4.1 Primary and secondary outcomes

Primary outcomes:

Evaluation of the % regression of migraine episodes with aura in relation to platelet reactivity in migraine patients, with and without aura, carriers of PFO, together with the dosage of PGE1, PGE2, serotonin and cytokines in order to identify potential predictive markers of beneficial effect of PFO correction on migraine symptoms.

Secondary outcomes

1. Reduction in the number of migraine days compared to pfo pre-correction, FU at 6 and 12 months.

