Patients will receive 70 IU/Kg of heparin at the beginning of the procedure in order to maintain the ACT (activated platelet aggregation time) value > 200 seconds. Aspirin 100 mg will already be therapy in place for more than 7 days and continued for at least 6 months after the correction of PFO while Clopidogrel 75 mg will be administered immediately after the procedure and continued for 2-3 months in patients treated with implantation of devices > 25 mm diameter. Antibiotic prophylaxis will be started before the procedure and continued for the next 5 days.

FOLLOW-UP

The clinical and diagnostic follow-up with cardiological examination, color-Doppler echocardiogram at 6 and 12 months and compilation of the Migraine severity score scale (Table 1), will allow to evaluate any residual shunts post correction of PFO and the beneficial effects on the control of migraine symptoms by reassessment of the Anzola score.

Phase 2: Analysis of platelet reactivity and levels of inflammatory cytokines, PGE1, PGE2 and serotonin in migraine patients with PFO.

Estimated time: 24 months

This phase of the study aims to investigate whether the beneficial effect of PFO correction on migraine is secondary to a barrier mechanism to platelet microembolization and that this response may correlate with the parameters of platelet function and activation. For this purpose, the study of platelet function will be carried out before the correction of PFO and 180 days after surgery.

For the evaluation of the parameters of platelet function from each patient, a blood sample will be taken in the absence of stasis, in order to avoid platelet activation, from the antecubital vein of the forearm by means of a G19 needle. Before proceeding with the separation of the platelets, a quantitative hematology analysis will be performed with leukocyte formula and platelet count by means of Sysmex XS 1000 automatic blood count.

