8.4 Type and duration of subjects following adverse events

9. statistical analysis

9.1 statistical analysis

Continuous variables will be summarized using the DS \pm mean. Categorical variables are represented using frequencies and percentages. For the comparison between responders and non-responders, the Student's 2-code t-test or the Wilcoxon test for continuous variables will be used. The Chi-square test or the Fisher test will be used for categorical variables.

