9.2 Calculation of the sample number

The sample size calculation is based on the 1-year primary endpoint. A value for the frequency of reaching the primary endpoint was placed around 60%, in accordance with the data reported in

Protocol number

NCT03521193

literature^{22, 27}. A sample of 92 patients was identified, necessary to obtain a potency of 80% able to detect as significant ($p < 0.01$, considering the Bonferroni correction for multiple tests) a correlation coefficient of 0.35 (adjusted for 4 confounding variables) between the variation of the migraine score sec. Anzola and any of the 5 factors (platelet reactivity, PGE1, PGE2, cytokines, serotonin) measured at baseline.

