9.3 Significance level to use

Statistical significance will be considered that obtained with a p value of 0.05.

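### The 80% power stated for 92 patients belongs to an adjusted correlation with change in Anzola score, which is neither the analysis listed in section 9.1 nor the primary outcome named in section 4.1

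*Combined protocol and SAP*

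**What the plan says.** Four sections of the combined protocol and SAP bear on the primary analysis.

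- **Section 4.1** names the primary outcome as "Evaluation of the % regression of migraine episodes with aura in relation to platelet reactivity in migraine patients, with and without aura", alongside prostaglandin, serotonin and cytokine measurements, so as to find markers that predict benefit. It gives no time point for this outcome.
- **Section 9.2** says "The sample size calculation is based on the 1-year primary endpoint" and that "A value for the frequency of reaching the primary endpoint was placed around 60" per cent. It then gives 92 patients for 80% power at p < 0.01, "considering the Bonferroni correction for multiple tests". The effect to be detected is a correlation of 0.35, adjusted for four confounders, "between the variation of the migraine score sec. Anzola and any of the 5 factors". The confounders are not named.
- **Section 9.1** gives descriptive summaries and then: "For the comparison between responders and non-responders, the Student's 2-code t-test or the Wilcoxon test for continuous variables will be used". Chi-square or Fisher tests are added for categorical variables.
- **Section 9.3** says: "Statistical significance will be considered that obtained with a p value of 0.05".

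Two parts of section 6.1 are also relevant. Step 1 speaks of classing patients as responders or non-responders according to regression of migraine or aura, without a numerical cut-off. The Follow-up paragraph says that the 6- and 12-month visits will assess "the beneficial effects on the control of migraine symptoms by reassessment of the Anzola score". Section 7.1 has headings only in this copy, so nothing is inferred from it.

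**The concern.** A sample size calculation supports a study only if the outcome, test and significance level it assumes are the ones that will be used. Here the response variable in 9.2 (change in Anzola score) is not the one in 4.1 (regression of aura episodes). The adjusted correlation in 9.2 does not appear in 9.1. The 60% in 9.2 suits a binary responder endpoint but is not an input to a correlation calculation.

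Two things are at stake. A reader who takes 80% as the power of the listed analysis is misled. And with more than one candidate outcome, test, responder cut-off and level, the choice could be made after the data are seen. In a search for predictive markers, that is how false leads arise.

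**Working it through.** **Inputs.** From 9.2: N = 92, power 80%, r = 0.35, four covariates, five factors, p < 0.01. From 9.3: 0.05. The t-test in 9.1 is two-tailed, so two-sided levels are used. Note that 0.05/5 = 0.01.

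**1. Reproducing the plan's figure.** By Fisher's z, with k covariates:

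N = [(z₁₋α/₂ + z₀.₈₀) / atanh(r)]² + 3 + k

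With atanh(0.35) = 0.3654, z₀.₉₉₅ = 2.576 and z₀.₈₀ = 0.842, the squared term is (3.417/0.3654)² = 87.45.

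- k = 0: 90.45, so 91 patients.
- k = 4: 94.45, so 95 patients.

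Power at N = 92 is Φ(0.3654 × √(92 − 3 − k) − 2.576):

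- k = 0: Φ(3.448 − 2.576) = 80.8%.
- k = 4: Φ(3.369 − 2.576) = 78.6%.

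Simulation of the correlation test gives 81.1% and 79.0%. By the same formula, two-sided 0.05 would need only 62 to 66 patients, and one-sided 0.01 only 79 to 83. So 92 matches the two-sided 0.01 correlation design and none of these alternatives.

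**2. Comparing the sections.**

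| | Response variable | Method | Level |
|---|---|---|---|
| 4.1 | Regression of aura episodes | Not stated | Not stated |
| 9.1 | Responder status, no cut-off | t-test/Wilcoxon, Chi-square/Fisher; no covariates | Not stated |
| 9.2 | Change in Anzola score (and an unused 60%) | Correlation, four covariates | 0.01 per factor |
| 9.3 | Not stated | Not stated | 0.05 |

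The marker list is the same in 4.1 and 9.2. The mismatch lies in the response variable and the method.

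**3. Power of the listed t-test.** This needs assumptions that the documents do not supply: a responder is a patient above a cut on Anzola change, 60% respond, marker and change are bivariate normal, and the correlation of 0.35 holds without adjustment. Splitting the change at that cut gives a marker-to-group correlation of

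0.35 × φ(0.253) / √(0.6 × 0.4) = 0.35 × 0.3863 / 0.4899 = 0.276,

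and a standardised difference of 0.276 / (0.4899 × √(1 − 0.276²)) = 0.586. With 55 responders and 37 non-responders:

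| Two-sided level | Noncentral t | Simulation | N for 80% power |
|---|---|---|---|
| 0.01 | 55.2% | 54.5% | about 145 to 147 |
| 0.05 | 77.9% | 77.3% | about 98 |

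For responder rates from 40% to 80%, power at N = 92 runs from about 42% to 56% at 0.01 and from about 67% to 79% at 0.05.

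**4. Error rate if 0.05 is used for each factor.** For five independent null factors, 1 − 0.95⁵ = 22.6%, against 1 − 0.99⁵ = 4.9% at 0.01. If the markers correlated at 0.5 (an assumption), the first figure would be about 18%.

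**5. Number of tests.** Section 6.1, Phase 2, lists three cytokines and many platelet readouts. If the cytokines were tested separately, with one platelet measure, there would be seven tests at 0.05/7 = 0.0071. The adjusted correlation would then have about 75% power at N = 92.

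**The case against.** The best reply is that the plan is more coherent than the table suggests, and several parts of that reply stand.

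- **Level.** A reader might infer that 9.3 contradicts 9.2 and drops the multiplicity correction. The documents do not establish this. Since 0.05/5 is exactly 0.01, 9.3 may be the overall level from which 9.2 takes its per-test level. What remains is that 9.3 does not say which it is.
- **Outcome.** A reader might infer two unrelated primary outcomes. The Anzola table in 6.1 has frequency and aura items, so change in the score partly reflects regression of aura episodes, and follow-up benefit is assessed by that score. The two variables overlap but are not the same, and no passage makes the Anzola score primary.
- **Patients without aura.** A reader might infer that the 4.1 outcome is undefined for them. That holds only for a percentage change within each patient. The phrase can also mean the share of patients with regression, which fits the 60%, Step 1 of 6.1 and the 9.1 tests. On that reading the Anzola correlation is the odd one out, and the mismatch with 9.2 remains. Any loss of power from restricting to patients with aura cannot be sized, because the documents give no aura share.
- **Design.** This is a single-centre observational study looking for potential markers. That lowers the stakes, but 9.2 still claims 80% power with a Bonferroni correction, and that claim should match the analysis.

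**Conclusion.** The point holds. The 80% power in 9.2 belongs to an adjusted correlation with change in Anzola score. Section 9.1 does not list that analysis and 4.1 does not name that response variable. Following 9.1 as written does not deliver the stated power at 0.01.

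The number 92 is not itself in error. It is three short of the 95 that Fisher's z gives with four covariates, which costs about one percentage point of power.

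The size of the shortfall rests on the cut-off, responder rate and normality assumed above. The Anzola score is a short sum of banded items, so normality is an idealisation. A reader might add the figures together, but they are alternatives: about 54-55% power goes with testing at 0.01, while about 77-78% power and the 23% false-positive chance go with testing each factor at 0.05. The 23% also depends on reading 9.3 as a per-test level.

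Nor do the documents show that change in Anzola score is the right primary outcome. That it fits the sample size is not a reason to prefer it.

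**What to change.** Make 4.1, 9.1, 9.2 and 9.3 describe one primary outcome, time point, test and level. The investigators should choose between two routes before analysis:

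- **(a) Anzola route.** Name 12-month change in Anzola score as primary in 4.1. Add the adjusted correlation or regression to 9.1, naming the four covariates and one measure for each of the five factors. Restate the power in 9.2 as about 79% for 92 analysed migraine patients. The word analysed matters because 9.2 states no dropout allowance, and migraine because the criteria listed in 5.1 do not require it.
- **(b) Responder route.** Keep the 4.1 outcome and the 9.1 tests. Define the responder cut-off, the time point and who is evaluable for aura. Restate the power in 9.2 for that test.

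Under either route, say in 9.3 that 0.05 is the family-wise level and 0.01 applies to each of the five factors. Say what the 60% is for, or remove it.

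The cost is text changes and a protocol amendment, which section 18 makes subject to Ethics Committee approval. Route (a) displaces the outcome that 4.1 now names and rests on a banded score. Route (b) means a lower stated power at 92 patients, or a larger sample: about 145 to 147 under the assumptions above. Those assumptions carry over a correlation set for the Anzola score, so (b) needs its own effect size.

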5.1 Inclusion criteria

Patients aged > 18 years will need to meet 2 or more criteria:

1. previous Stroke o TIA
2. Positive MRI for ischemic outcomes –
3. presence of PFO with dx-sin shunt in basal conditions > 10 MES and during Valsalva > 20 MES
4. SIA aneurysm or residual Chiari network/Eustachian valve
5. Positive Thrombophilic screening (MTHFR/prot C/Prot S)
6. ability to sign informed consent for participation in the study and adhere to the planned clinical follow-ups

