5.3 Criteria for withdrawal

5.4 Informed consent

It is the responsibility of the researcher to obtain written informed consent from the participants before inclusion in the study, after a full explanation of the nature, objectives and risks inherent in participation in the study. The methods of processing personal data and clinical information obtained will also be explained to each participant; the participants in the study will sign the consent to the processing of personal data. It will also be emphasized that participation in the study is voluntary and it will be possible to interrupt it at any time or request at any time the elimination of any biological information or material obtained for research purposes.

6 Treatment of patients

1. 6.1 Treatment/Procedures and evaluations planned during the study

The study, which will take place at the [REDACTED], will be divided into two phases, described below.

Step 1: Screening of symptomatic PFO patients for migraine with aura initiated percutaneous PFO correction and clinical follow-up.

Estimated time: 24 months

This phase of the study aims to test the hypothesis that the population of subjects with PFO and indication to percutaneous correction of the defect, when symptomatic for migraine with or without aura, can be characterized as responders or non-responders with regression of the migraine symptomatology / aura.

The identification of symptomatic patients for migraine, after preliminary neurological evaluation, will be accompanied by a classification of migraine according to the severity scale of migraine sec. Anzola (Table 1). This evaluation will be repeated after PFO correction and outpatient clinical follow-up at a distance of 6 and 12 months, together with the execution of color-Doppler TT echocardiogram. This last examination will characterize the correct positioning of the PFO occlusive device and the presence/absence of residual inter-atrial shunt dx-sin.

TABLE 1. Migraine Severity Score

Intensity
0=No pain
1=Moderate (does not interfere with the performance of daily activities)
2=Severe (interferes with the performance of daily activities)
3=Inbearable (requires enticing)
Duration

Protocol number

NCT03521193

0=No pain

1=<6 hours

2=6–12 hours

3=>12 hours

Frequency

0=No pain

1=1–4/month

2=5–9/month

3=>10/month

Aura

0=No aura

OCCLUDER DEVICE FOR PFO

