7.1 Specifying Effectiveness/Endpoint Parameters

Primary endpoints:

Secondary endpoints

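### The primary outcome in section 4.1 has no value for patients without aura, whom it explicitly includes, and section 9.2 sizes the study on a different variable

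*Combined protocol and SAP*

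**What the plan says.** Section 4.1 states the primary outcome as "Evaluation of the % regression of migraine episodes with aura in relation to platelet reactivity in migraine patients, with and without aura". The same sentence gives its purpose as "in order to identify potential predictive markers of beneficial effect of PFO correction on migraine symptoms", which is wider than aura.

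Section 6.1 describes the Step 1 population in two ways. Its heading reads "Screening of symptomatic PFO patients for migraine with aura initiated percutaneous PFO correction and clinical follow-up". Its hypothesis concerns patients who, "when symptomatic for migraine with or without aura, can be characterized as responders or non-responders with regression of the migraine symptomatology / aura".

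Other parts of the protocol bear on the point:

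- **Section 5.1** opens with "Patients aged > 18 years will need to meet 2 or more criteria". None of the six criteria listed is migraine or baseline aura, so patients without aura can enter.
- **Section 7.1** carries headings for primary and secondary endpoints with no text under them. Section 9.5, on missing or spurious data, is also a heading only.
- **Section 9.1** compares responders with non-responders. No response cut-off is given there or elsewhere.
- **Section 9.2** says the calculation rests on the one-year primary endpoint: "A sample of 92 patients was identified, necessary to obtain a potency of 80% able to detect as significant" (at p < 0.01) a correlation of 0.35, adjusted for four unnamed variables. The correlation is between the change in Anzola score and any of five baseline factors.
- **Table 1 in section 6.1** builds the Anzola score from intensity, duration, frequency and aura.
- **The secondary outcome in 4.1** is the reduction in migraine days at 6 and 12 months.

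**The concern.** A percentage regression needs a non-zero baseline. Section 4.1 counts only episodes with aura, yet applies the count to patients who may have none. Read literally, a patient without aura whose headaches stop completely is either unscorable or a non-responder. A patient with aura who loses the aura but keeps every headache scores 100% regression.

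The marker analysis is meant to show who benefits from closure. If its outcome is undefined for part of the population, someone must decide later how to treat those patients. The choices are to exclude them, to count them as failures, or to switch to the Anzola score. Each gives a different analysis set and possibly a different answer, and nothing in the plan fixes the choice before results are seen.

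**Working it through.** **1. The outcome as worded.** With B aura episodes at baseline and F at follow-up, regression = 100 × (B − F)/B.

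- B = 0, F = 0: 0/0, undefined.
- B = 0, F > 0: a negative number divided by zero, undefined.
- B > 0, F = 0: 100%, whatever happens to headaches without aura.

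**2. The places that could settle it.**

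| Section | Variable | Population |
|---|---|---|
| 4.1 | % regression of aura episodes | with and without aura |
| 6.1, Step 1 heading | none | with aura |
| 6.1, Step 1 hypothesis | regression of migraine symptoms / aura | with or without aura |
| 7.1 | no text | no text |
| 9.2 | change in Anzola score | all 92 |

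No two of these rows give the same variable for the same population.

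**3. Reproducing the 92.** Inputs from 9.2: r = 0.35, p < 0.01 (0.05/5), power 80%, four adjustment variables. Sidedness is not stated; I take two-sided. By Fisher z, n = ((2.576 + 0.842)/atanh 0.35)² + 3 + k, with atanh 0.35 = 0.3654.

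- k = 0: 87.45 + 3 = 90.45, so 91.
- k = 4: 87.45 + 7 = 94.45, so 95.

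The stated 92 lies between these. Power at 92 is 80.8% (k = 0) or 78.6% (k = 4). The figure is sound for the Anzola variable, and the 60% endpoint frequency quoted in 9.2 does not enter it.

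**4. If patients without aura count as non-responders.** The background section reports septal aneurysm in 28% of migraine patients with aura and 3.6% of those without. Suppose 60% of aura patients respond (borrowing 9.2's frequency), aneurysm has no real link with response, and a share p has no aura. Responders then all have aura, so 28% have an aneurysm. Among non-responders the proportion is (0.4(1 − p) × 0.28 + p × 0.036)/(0.4(1 − p) + p).

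- p = 0.30: (0.0784 + 0.0108)/0.58 = 15%.
- p = 0.50: (0.056 + 0.018)/0.70 = 11%.

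Aneurysm would look like a predictor of response through aura status alone.

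**5. If patients without aura are excluded.** The documents give no share without aura, so 20% to 50% is an assumption. So is carrying r = 0.35 over to a variable for which it was not chosen. Power = Φ(0.3654 × √(N − 7) − 2.576).

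| Share without aura | N | Power |
|---|---|---|
| 0% | 92 | 79% |
| 20% | 92 × 0.8 = 74 | 66% |
| 30% | 92 × 0.7 = 64 | 57% |
| 40% | 92 × 0.6 = 55 | 48% |
| 50% | 92 × 0.5 = 46 | 38% |

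A noncentral F calculation gives values 4 to 6 points higher in each row (83% at 92, 44% at 46), with the same pattern.

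**6. If the Anzola score is used.** A patient without aura scores 0 on that item and still has values for intensity, duration and frequency. Nobody is lost for lack of aura.

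**The case against.** The strongest answer is that 9.2 already contains the remedy. The only analysis with a stated effect size, significance level and power uses the change in Anzola score, which every migraine patient has. The text reads as a rough translation, so the aura wording in 4.1 may be a slip. Headache benefit without aura is also captured by the secondary outcome of migraine days. Loss of aura is a legitimate endpoint in its own right, and the Step 1 hypothesis is broad enough for a patient without aura to be a responder.

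Much of this stands, and it narrows the point to a conflict between sections. It does not remove the conflict. Section 9.2 claims to size the primary endpoint, 4.1 names another variable, and nothing says which governs. Under either reading the text must change.

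A reader might infer three stronger things that the documents do not support:

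- **That the study is underpowered or 92 is wrong.** The 92 reproduces for the Anzola change. The losses in step 5 require exclusion, an assumed share, and an r borrowed from another variable.
- **That the five primary markers are confounded by aura.** No section reports that platelet reactivity, PGE1, PGE2, cytokines or serotonin differ by aura status. The four adjustment variables are unnamed, so baseline aura is neither confirmed nor ruled out among them.
- **That Eustachian valve and Chiari network differ by aura status.** The figures given (100% against 55%) compare migraine with aura against people without migraine. Only septal aneurysm and shunt extent are reported by aura status.

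**Conclusion.** The point holds as a defect of definition. The primary outcome worded in 4.1 cannot be computed for patients without aura, whom the same sentence includes, and 9.2 attaches the sample size to a different variable. That much follows from the text and needs no assumption.

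The consequences are conditional on applying 4.1 literally. Counting these patients as non-responders could make septal aneurysm or shunt extent appear predictive through aura status; in the illustration, aneurysm is 28% in responders against 15% or 11% in non-responders. Excluding them would leave 74 to 46 patients and power of about 66% to 38%, for an assumed share of 20% to 50% and an unchanged r of 0.35. If the Anzola change is the intended primary variable, neither consequence follows from the definition itself, and the correction is to say so. It should be made before analysis, because the present text leaves the choice of primary variable open.

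**What to change.** 1. State in 4.1 and 7.1 that the primary outcome is the change in total Anzola score from baseline to 12 months in all migraine patients, the variable 9.2 already sizes for.
2. Make the percentage regression of aura episodes a secondary outcome, restricted to patients with aura at baseline.
3. Name baseline aura (yes/no) as one of the four adjustment variables in 9.2, and adjust for it or stratify by it in the anatomical-predictor analyses.
4. Make the Step 1 heading and hypothesis in 6.1 describe the same population.

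The cost is protocol wording. Table 1 already has an aura item, and the sample size need not change. The downside is that the aura-specific claim becomes a smaller secondary analysis; migraine days remain a secondary outcome.

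If the sponsor does want aura regression as primary, that analysis must be restricted to patients with baseline aura and sized on their number. To have 92 of them at an assumed 20% to 50% without aura, enrolment would be 92/0.8 = 115 to 92/0.5 = 184, and the effect size would need its own justification.
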